2.1. End points

2.1.1. Primary Endpoint

Demonstration of the feasibility and safety of delivering a radiation treatment using the GammaPodTM for patients undergoing breast conserving therapy ensuring coverage of the target volume with appropriate dose homogeneity and conformity as defined in the study.

2.1.2. Secondary Endpoints

- The evaluation of overall patient comfort in the GammaPodTM procedure.
- The evaluation of acute toxicity during and up to 1 month after GammaPodTM TB boost.
- The evaluation of long-term toxicity at one year to assess the presence of subcutaneous fibrosis, and fat necrosis.
- The evaluation of the use of Hollister Medical Adhesive spray for sealing the cup flange during radiation therapy and its effects, if any, on the patient's skin

3. Patient Selection Criteria:

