5.5.6. Timing

Treatment to the whole breast will begin within 7-8 days from the tumor bed boost (GammaPodTM) treatment unless an adverse event occurred from the GammaPod treatment.

6. Surgical Resection

- Lumpectomy and lymph node sampling or dissection should be performed according to institutional standard of care.
- Surgical clips to delineate the surgical bed is the standard of care of our referring surgeons.

7. Adjuvant Systemic Therapy

- Chemotherapy and/or hormonal therapy may be given pre-operatively or post-operatively according to standard of care and will be recorded.
- Hormonal therapy, if used, will be delivered concurrently and recorded.

8. Pathology

Pathology assessment of the lumpectomy and lymph node assessment will follow current standard of care.

9. Patient Assessments

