9.1. Study parameters

Assessment	Pre-Entry	During Radiation	At 6 weeks ^e	At 6 months ^e	At 1 year ^e
H&P, Breast Exam	X		X	X	X ^d
Weight	X			X	X ^d
Bra cup size	X			X	X
Disease status	X		X	X	X ^d
Mammograms	X			X ^f	X ^c
Toxicity		X ^b	X ^b	X ^b	X ^b
Photographs	X ^a	X ^a		X ^a	X ^a

a. Photographs will be obtained prior to GammaPod treatment, following the removal of the breast immobilization device after the treatment is delivered, on the day whole breast radiation starts and on the last day of treatment as well as at their 6 and 12 month follow up.

b. Patients will be seen on day of GammaPod treatment and following GammaPod treatment on day of 1st whole breast treatment, then weekly during whole breast radiation and all toxicity will be recorded at each of the time points or more often as clinically indicated.

c. Yearly thereafter

d. Clinical examination and disease status assessment at 6-month intervals for the first 3 years, and yearly thereafter

e. Time points are from the start of radiation therapy

f. Mammogram 6 months after radiation therapy, then yearly thereafter.

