9.2.2. Toxicity reporting

Acute radiation effects will be evaluated and scored using the NCI CTCAE v. 4.0. A copy of the CTC version can be downloaded from the CTEP homepage (<http://ctep.info.nih.gov>). Please note that this study will not be using separate toxicity scales for acute and late radiation effects. All acute effects and late effects that occur within one year will be recorded in ONCORE. Data and safety monitoring will be reported to the in-house data safety monitoring board bi-annually.

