9.2.5. Fatal events (Grade 5)

All deaths with the attribution of definitely, possibly, or probably related to protocol radiation therapy must be reported according to IRB reporting policy. Every Severe Adverse Event (SAE) will be reported on FDA 3500 A (MedWatch Form). All deaths during and within 30 days of completion of protocol radiation therapy, regardless of attribution, must be reported according to IRB reporting policy. Every Severe Adverse Event (SAE) will be reported on FDA 3500 A (MedWatch Form)

<https://www.accessdata.fda.gov/scripts/medwatch/>

If the event is more than 30 days from completion of radiation treatment, but is felt to be definitely, possibly, or probably resulting from protocol radiation therapy, this event must be reported according to IRB reporting policy. Every Severe Adverse Event (SAE) will be reported on FDA 3500 A (MedWatch Form).

10. Statistical Considerations

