10.1. Objectives

The primary objective is to demonstrate the feasibility and safety of delivering a tumor bed boost dose using the GammaPod stereotactic system for patients undergoing breast conserving therapy. Primary feasibility endpoints will include an estimate of reproducibility of the radiation technique. Reproducibility will be assessed on the basis of radiation therapy being scored as acceptable, marginally acceptable, or unacceptable using the criteria described in Section 5.4.3. The proportion of patients eligible for a GammaPod TB boost will be based on clinical and pathological findings. Secondary safety endpoints will include the number and type of serious adverse device-related events, the incidence of acute radiation. Acute toxicity will be assessed using the NCI CTCAE v4.0 criteria. Toxicities will be defined as acute if they occur within one month of protocol therapy. TB boost is not experimental. Delivering a single large dose to the TB is also not new. Based on previous intracavitary, intraoperative TB irradiations with 20 to 21 Gy(30, 44-46), we do not expect elevated significant late side effects. To reiterate, this study will treat only to 8 Gy as opposed to 20 to 21 Gy and is treating a similar volume as other intraoperative experiences where thousands of patients have been treated. Subsequently, the late toxicity profile will not be part of the statistical evaluation in this feasibility study. However, toxicity will be reviewed at 12 months after the completion of the radiation therapy and the data will be captured. Acute effects may be related to placement of the immobilization device but since it is placed prior to the whole breast radiation, the one month post whole breast radiation endpoint is appropriate.

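### The acute toxicity endpoint has two conflicting windows: one month after the GammaPod boost (section 2.1.2) and one month after whole breast radiation (section 10.1)

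*Combined protocol and SAP*

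**What the plan says.** Section 2.1.2 gives the endpoint as "The evaluation of acute toxicity during and up to 1 month after GammaPodTM TB boost". The other timed toxicity endpoint in that list is a one-year assessment of subcutaneous fibrosis and fat necrosis.

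Section 10.1 gives the definition twice. It states: "Toxicities will be defined as acute if they occur within one month of protocol therapy". It then observes that effects of the immobilization device may contribute but that the device is placed before whole breast radiation, and concludes that "the one month post whole breast radiation endpoint is appropriate". The same section leaves late toxicity out of the statistical evaluation.

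On timing, section 5.5.6 starts whole breast radiation within 7-8 days of the boost, "unless an adverse event occurred from the GammaPod treatment". Section 5.5.2 allows 50 Gy in 25 fractions or 40 Gy in 15.

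On data collection, section 9.1 has patients seen on the boost day and on the first whole breast day, "then weekly during whole breast radiation and all toxicity will be recorded at each of the time points". Visits follow at 6 weeks, 6 months and 1 year, and for these "Time points are from the start of radiation therapy". Section 9.2.2 says that "this study will not be using separate toxicity scales for acute and late radiation effects", and acute and late effects within one year go into the study database.

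**The concern.** The sections anchor the same endpoint to different events, the boost and the end of whole breast radiation. The undefined term in section 10.1 does not reconcile them. If *protocol therapy* means the boost, that sentence contradicts the conclusion of section 10.1. If it means all study radiation, it contradicts section 2.1.2. No section takes precedence.

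Acute toxicity is a stated safety endpoint of a first-in-human device study, and its count depends on which section the analyst follows. A skin reaction that starts late in a 25-fraction course is acute under section 10.1. Under section 2.1.2 it falls outside the acute endpoint, and it does not belong to the one-year fibrosis and fat necrosis endpoint either. Left open, the choice could be made after the data are seen.

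**Working it through.** **Plan's own figures.** The plan gives none for these windows. Its only computed design figures are those of the Simon design (5/8, 13/17; 60% against 90%). Exact binomial calculation gives type I error 0.0436 (stated 4.4%), power 0.9045 (90.5%), early termination 0.685 (68%) and expected size 8 + (1 − 0.6846) × 9 = 10.84 (10.8). These are reproduced, and they use dose-distribution acceptability only, so the toxicity window does not enter.

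**Inputs.**
- Boost = day 0.
- Gap g to the first whole breast fraction: 1-8 days, reading the within 7-8 days of section 5.5.6 as an upper limit.
- Monday start: section 1.3 calls this standard practice.
- Five fractions a week: the introduction gives Monday to Friday for the standard course; assumed here for both schedules.
- No treatment breaks, and one month = 30 days (assumptions).

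**Formulas.**
- Last of 15 fractions: three weeks, so g + 2×7 + 4 = g + 18.
- Last of 25 fractions: five weeks, so g + 4×7 + 4 = g + 32.
- Section 2.1.2 window end: day 30.
- Section 10.1 window end: last fraction + 30, that is g + 48 or g + 62.

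| Gap g (boost day) | Last of 15 | 10.1 end, 15 | Last of 25 | 10.1 end, 25 | Fractions of 25 after day 30 |
|---|---|---|---|---|---|
| 1 (Sun) | 19 | 49 | 33 | 63 | 3 |
| 3 (Fri) | 21 | 51 | 35 | 65 | 5 |
| 4 (Thu) | 22 | 52 | 36 | 66 | 5 |
| 5 (Wed) | 23 | 53 | 37 | 67 | 5 |
| 6 (Tue) | 24 | 54 | 38 | 68 | 6 |
| 7 (Mon) | 25 | 55 | 39 | 69 | 7 |
| 8 (Sun) | 26 | 56 | 40 | 70 | 8 |

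Example for the last column, g = 7: the weeks start on days 7, 14, 21, 28 and 35. Days 31 and 32 of the fourth week and all five days of the fifth fall after day 30, giving 2 + 5 = 7.

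**Results.**
- The windows end 19-26 days apart with 15 fractions (49 − 30 to 56 − 30) and 33-40 days apart with 25 (63 − 30 to 70 − 30).
- With a Monday start, gaps of 1, 2 and 8 days would need a weekend boost. For weekday boosts (g = 3-7), 5-7 of the 25 fractions come after day 30. At 50/25 = 2 Gy each, that is 10-14 Gy.
- With 15 fractions the whole course lies inside the section 2.1.2 window, which closes 30 − 26 = 4 to 30 − 19 = 11 days after the last fraction. Onsets after day 30 and up to day 49-56 are still classified differently.

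**The case against.** **Little depends on it.** Acute toxicity has no test, threshold or stopping rule. The tolerance-based suspension rule in section 11 concerns complaints about the cup or prone setup. Toxicity is recorded throughout on one scale, so either window can be tabulated from the same data. All of this stands and sets the severity. A reader might infer that safety data are lost or that the trial's conclusion is at risk; the documents support neither.

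**Section 10.1 governs in practice.** Section 2.1.2 states an evaluation period, whereas section 10.1 states a definition and sits in the statistical section. This reduces the ambiguity. It does not remove it, because the definition rests on an undefined term and no precedence is stated.

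**A boost-anchored window suits a device study.** Whole breast radiation is standard of care (section 13), and a longer window counts more of its reactions. This is a fair reason to report a boost-specific summary as well. It does not make the two definitions compatible.

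**Two stronger readings are tempting.**
- Since the 6-week visit falls on about day 42-50, a reader might infer that any reaction first noted there lies outside section 2.1.2. That confuses visit date with onset. Section 10.1 speaks of when toxicities occur, and a reaction that began before day 30 can be first recorded at 6 weeks.
- Section 9.2.5 requires reporting of "All deaths during and within 30 days of completion of protocol radiation therapy", which a reader might take as proof that the section 10.1 anchor was intended. That rule governs reporting of deaths and does not define acute toxicity.

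**Conclusion.** The conflict is real and in current text. On the planned calendar the acute endpoint closes on day 30 under section 2.1.2, and on day 49-56 (15 fractions) or 63-70 (25 fractions) under section 10.1. With 25 fractions and a weekday boost, 10-14 Gy of the course is given after the earlier cutoff. Reactions with onset after day 30 and within 30 days of the last fraction are acute under one section only.

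The figures rest on the assumptions listed above. A later whole breast start, which section 5.5.6 permits after an adverse event from the boost, or a treatment break, would widen the difference. The documents give no reaction rates, so the number of patients reclassified cannot be stated. For scale, one patient among the full 17 is 1/17 = 5.9 percentage points.

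The consequence is confined to a descriptive secondary count. The primary dosimetric endpoint and the Simon design are unaffected. This is worth correcting before analysis, at low severity.

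**What to change.** Use one definition in both 2.1.2 and 10.1: CTCAE v4.0 events with onset from the GammaPod boost to 30 days after the last whole breast fraction. Put that wording in place of *protocol therapy* in section 10.1. It adopts the anchor that section 10.1 already justifies. State that events are classified by date of onset, not by the visit at which they are first noted.

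If a device-focused figure is wanted, tabulate events with onset up to 30 days after the boost as a separately named boost-specific summary from the same data.

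The cost is wording in two sections, with no new visit, scale or test. The downside is that the longer window counts more reactions due to whole breast radiation, so the main count is less specific to the boost; the separate summary partly answers this. One limit remains. With 25 fractions, the last scheduled visit inside the window is the 6-week visit, 20-28 days before it closes: (g + 62) − (g + 42) = 20 if that visit is timed from the first whole breast fraction, or 63 − 42 = 21 to 70 − 42 = 28 if timed from the boost. Later onsets would depend on unscheduled assessment or on dating at the 6-month visit.

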3.1. Eligibility criteria

- The patient must sign consent for study participation.
- The patient must be female and have a diagnosis of an invasive or non-invasive breast cancer that was treated surgically by a partial mastectomy.
- The patient must be deemed an appropriate candidate for breast conserving therapy (i.e. not pregnant, never had radiation to the treated breast, breast size would allow adequate cosmesis after volume loss from partial mastectomy).
- Patients with involved lymph nodes are candidates for the study as long as regional nodal radiation is not required by the treating physician.
- Surgical margins are negative for invasive or non-invasive breast cancer.
- The greatest dimension of the tumor is less than 4cm before surgery.
- The volume of the TB CTV is less than 25% of the whole breast PTV which is a criteria used for partial breast alone trials (NSABP B-39).
- Multifocal disease is allowed if it was removed by a single lumpectomy resection and the patient remained a candidate for breast conservation.
- Age 60 years and older.
- Women of childbearing potential must use an effective contraceptive method such as condom/diaphragm and spermicidal foam, intrauterine device (IUD), or prescription birth control pills. A negative pregnancy test must be obtained prior to study enrollment or waiver signed.
- The surgical cavity is clearly visible on CT images.
- The patient must weigh less than 150Kg (330lb), which is the limit of the imaging couch.

- The patient must be less than 6'6" in height.
- The patient must feel comfortable in the prone position.

3.2. Ineligibility criteria

- Patients with proven multi-centric carcinoma (tumors in different quadrants of the breast or tumor separated by at least 4 cm).
- Prior radiation therapy above the umbilicus
- Unable to fit into the immobilization breast cup with an adequate seal
- Male gender.
- Patient cannot comfortably be set up in the prone position (i.e. physical disability)
- Unable to fit into the breast immobilization device due to breast size or other anatomical reason.
- Mastectomy is the surgery performed.
- Patient has received prior radiotherapy to the involved breast.
- Regional nodal irradiation is part of the treatment plan.
- Tumor bed is less than 5 mm from the skin surface.
- Patients with skin involvement, regardless of tumor size.
- Patients with connective tissue disorders specifically systemic lupus erythematosis, scleroderma, or dermatomyositis.
- Patients with psychiatric or addictive disorders that would preclude obtaining informed consent.
- Patients who are pregnant or lactating due to potential exposure of the fetus to RT and unknown effects of RT to lactating females.

4. Registration

- Consent for enrollment onto protocol will be performed by principal investigator or member of research team.
- Patients can only be registered after eligibility criteria are met following the conventional supine CT simulation which may occur the day of the simulation or within a few days such that GammaPod treatment could be planned prior to whole breast radiotherapy. The conventional supine or prone CT simulation used for whole breast radiotherapy is performed approximately 7-10 days prior to starting whole breast radiotherapy.

- Once a patient is registered, a case number will be assigned to the patient.

5. Radiation Therapy Protocol

5.1. CT simulation for planning whole breast irradiation

The patient will undergo a conventional CT simulation in supine or prone position without the breast immobilization cup. The purpose of the CT simulation is two-fold: 1) we will see if the TB volume can be accurately delineated and if the TB volume is too large for GammaPod boost; and 2) the CT images are used for planning the patient's whole breast irradiation. If, after viewing the CT images and the patient is deemed a study candidate and consents, they will receive a second CT-sim and the GammaPod TB boost treatment on the same day as described below.

5.2. CT-based treatment planning for the GammaPod treatment

- Patients will be simulated in the prone position using a breast immobilization cup supplied by Xcision. Depending on the fit of the cup, supplemental silicone fillers and supplemental silicone adhesive are used to improve fit and seal of the cup. The cup consists of two layers with an air space in between. A small negative pressure (fixed at -150 mmHg and not adjustable) is applied between the 2 layers to immobilize the breast inside the cups.
- The reproducibility of the breast immobilization cup decreases outside the confines of the cup (Figure 3), such that if any "tumor bed" clip is above the rim of the cup, the patient will not receive treatment with the GammaPod and will be treated off study using departmental standard treatment.
- The CT will start at the thyroid notch and extend below the infra-mammary fold (including the entire lung) with a slice thickness of 1.0 mm through the breast

[figure not shown]

Figure 3. For a patient to be included in the study, all clips need to be below the yellow line demarcated as top of the breast immobilization cup. The image shown here represents a patient ineligible for the study, as would any patient where any clip is above the line.

5.3. Target volumes for TB boost

The following structures will be outlined on all CT slices: the clinical target volume (CTV) and the planning target volumes (PTV).

5.3.1. *Clinical Target Volume (CTV)*

The CTV will be the tumor bed which is the combination of the surgical changes (surgical cavity) and surgical clips in the surgical bed + 5 mm. This margin incorporates the extent of anatomy that is considered to be required clinically to be covered by the prescribed dose.

5.3.2. *Planning Target Volume (PTV)*

- The PTV will provide a margin around the CTV to compensate for uncertainty in treatment set up as determined by GCC1047. This study indicates that uncertainty of target position within the stereotactic coordinate system is within 3 mm to two standard deviations. A further 2 mm margin will be used for this study to capture any residual uncertainty due to respiratory motion of the breast and any uncertainty in the positioning of the stereotactic coordinate system relative to the beams.

- The PTV expansion will be defined as a uniform 5 mm expansion of CTV.
- The PTV will be limited to 5 mm from the skin surface and 0 mm from the pectoralis muscle posteriorly.

5.4. Treatment planning for tumor bed boost

The PTV will be used as the target for treatment planning

5.4.1. Dose prescription and delivery

The PTV will receive 8 Gy in 1 fraction.

5.4.2. Dose limitations for normal tissues.

- The dose at the skin surface must be less than 95% of the prescription dose.
- The dose at 1 cm from the PTV should be less than 30% of the prescription dose.
- The chest wall will receive less than the prescription dose.
- No rib should receive more than 75% of the prescription dose.
- The maximum dose to lung should be no more than 2.5Gy. This limit is slightly less than the single fraction dose given in hypofractionated whole breast irradiation (3.3Gy in START trial(18) and 2.66Gy in Ontario trial(16)).
- The maximum dose to the heart should be no more than 2.5Gy. This limit is slightly less than the single fraction dose given in hypofractionated whole breast irradiation (3.3Gy in START trial and 2.66Gy in Ontario trial).

5.4.3. Criteria for judging deviations from plan

- No deviation (acceptable): 100% prescription isodose surface covers at least 95% of the PTV. Maximum dose to the PTV should not exceed prescription dose by >20%. Minimum dose to the PTV should not be lower than 7.6Gy (below the prescription dose by 5%). All specified critical normal tissue DVH limits as described in 5.4.3 have been met. As compared with TB boosts with FDA approved brachytherapy techniques and intraoperative treatments, which are associated with dose “hot spots” of 100% - 400%, a 20% dose inhomogeneity within the TB PTV should be acceptable.
- Minor deviation but acceptable: 95% prescription isodose surface covers between 95% and 100% of the PTV. No portion of the PTV receives <93% of the prescription dose. Maximum dose to PTV exceeds prescription dose by >20% but <30%. All specified critical normal tissue DVH limits fall within 5% of the guidelines.
- Major deviations (unacceptable): 95% isodose surface covers < 95% of the PTV. A portion of PTV receives < 93% of prescription isocenter dose. Maximum dose to PTV exceeds prescription dose by >30%. Any critical normal tissue DVH limit exceeds 5% of the specified value.
- If a major deviation is required for treatment delivery, then the Gamma Pod treatment will not be delivered and the patient will be taken off study.

- Treatment delivery will not be performed if the seal of the breast cup is lost or pressure falls below a pre-determined value following the CT simulation. Such an event will be recorded.
- If the cup pressure drops to below 100 mmHg, which is signified by an alarm on the pump, the physician will do the following:
 - If it occurs before the simulation CT scan, continuation with the study should proceed once pressure is reestablished.
 - If pressure loss occurs following the simulation CT scan and before treatment, the CT simulation will need to be repeated to ensure the reproducibility of target position between CT scanning and treatment. The event will be recorded and the treating physician will decide whether to proceed with GammaPod treatment or treat the patient conventionally off study.
- Treatment delivery will not be performed if the breast cup cannot be locked into the treatment table. Such an event will be recorded.
- Treatment delivery will not be performed if the patient feels uncomfortable following the placement of the breast cup. Such an event will be recorded.

